5.2.3.2. Treatment Failure Rules

A participant who meets one or more of the treatment failure criteria specified in Section 5.2.3.1 will be considered a treatment failure from that point onward. The baseline values will be used for all directly measured endpoints regardless of the actual measurements. Zero will be assigned to improvement, and non-responder status will be assigned to binary response variables. However, treatment failure rules for the HSSD pain related endpoints will be handle differently and are specified in Section 5.2.3.2.1.

Treatment failure is assumed to have occurred at the earlier of the following dates:

- Date of discontinuation of study treatment due to lack of efficacy or an AE of worsening of HS or
- Date of initiation of a protocol-prohibited medication/therapy during the study that could improve HS.

In addition, lesions that received intervention as rescue therapy will be counted as present after the visit of intervention.

5.2.3.2.1. Treatment Failure Rule for HSSD Pain Related Endpoints

Participants who received analgesic therapy for HS within 1 day of a scheduled visit, will be considered a treatment failure for the HSSD past 24 hours pain and current pain endpoints at that visit. Treatment failure rules will not be applied throughout the study for analyses of the HSSD 7 days recall pain component.

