Participants who discontinue study intervention due to lack of efficacy or an AE of worsening of HS, or who started a protocol-prohibited medication or therapy during the study that could improve HS are considered treatment failures. The baseline values will be assigned regardless of the observed data for continuous endpoints, zero will be assigned to improvement and percent improvement, and nonresponders status will be assigned to binary response variables. Lesions that received intervention will be counted as present after the visit of intervention. After applying the treatment failure rules, the remaining missing data will be assigned nonresponders status for binary variables. For the longitudinal analyses, missing data handling rules will not be applied.

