5.2.2.5. Patients Reported Outcomes

5.2.2.5.1. Hidradenitis Suppurativa Symptom Diary

The HSSD (Section 10.11 of the protocol [Appendix 11]) is a 7-item patient self-reported questionnaire that assesses 5 HS-related symptoms including pain, tenderness, hot skin feeling, odor, and itchiness. The participants are asked to rate the severity of each symptom on a 0 to 10 numerical rating scale, with 0 indicating no symptom experience and 10 indicating the worst possible symptom experience. All 5 symptoms have a recall period of the past 7 days, except for 2 additional questions on pain which evaluate current pain and pain in the past 24 hours. Each individual symptom scale score, ranging from 0-10, will be summarized. A total symptom score, which will also range from 0-10, will be derived by averaging the 5 individual scale scores that utilize the past 7-day recall period.

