5.2.3.1. Treatment Failure Criteria

Participants who discontinue study intervention due to lack of efficacy or an AE of worsening of HS, or who started a protocol-prohibited medication or therapy during the study that could improve HS, are considered treatment failures.

The particular protocol-prohibited medications/therapies include:

Systemic Therapies:

- Any immunodulatory biologic therapy
- Any conventional systemic immunosuppressive therapy
- Any systemic corticosteroid for HS
- Any systemic antibiotic therapy for HS or any indications other than infection
- Any systemic retinoid

- Investigational Agents for HS
- Analgesic therapy for HS (Section 5.2.3.2.1)
- Phototherapy (PUVA and/or UVB) for any indications and other phototherapies for indication of HS

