5.2.4.1. Composite Strategy

The Composite Strategy assesses the treatment effects not only based on the variable measurements, but also based on intercurrent event defined in TF criteria. If a participant meets TF criteria, participant will be a non-responder for binary response variables and no improvement will be assigned for continuous variables.

- **Composite Estimand (Continuous)**

Variables: The endpoint is defined as change for baseline score. No improvement (zero change) will be assigned after a subject meets one or more treatment failure criteria.

Intercurrent Events: the intercurrent events are captured through variable definition.

Population level summary: difference in mean changes from baseline between a guselkumab group and placebo group.

- **Composite Estimand (Binary)**

Variables: The endpoint (e.g. HiSCR) is defined as the proportion of participants achieving a response. No responder status will be assigned after a subject meets one or more TF criteria.

Intercurrent Events: the intercurrent events are captured through variable definition.

Population level summary: difference in proportion of responders between a guselkumab group and placebo group.

The composite strategy will be used for analyzing all efficacy endpoints.

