5.5.7.2. Hidradenitis Suppurativa Symptoms Diary (HSSD)

- The change from baseline in each HSSD symptom scale score (7 days recall) and the change from baseline in current pain at Week 16 will be compared between each of the guselkumab groups and the placebo group.
- The change from baseline in HSSD total symptom score at Week 16 will be compared between each of the guselkumab groups and the placebo group.
- Number of participants with a reduction of $\frac{1}{2}$ SD or more from baseline in HSSD total symptom score at week 16 will be compared between each of the guselkumab groups and the placebo group.
- The change from baseline in each HSSD symptom scale score (7 days recall), the change from baseline for the past 24 hours pain and current pain, and the change from baseline in HSSD total symptom score will be summarized over time.

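### The SAP waives every treatment-failure rule for HSSD 7-day recall pain, against its own composite estimand, and leaves the HSSD total score undefined for treatment failures

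*SAP*

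**What the plan says.** **Who is a failure.** SAP 5.2.3.1 counts discontinuation for lack of efficacy or worsening HS. It also covers participants "who started a protocol-prohibited medication or therapy during the study that could improve HS, are considered treatment failures". Its list of prohibited therapies includes HS analgesics, with a pointer to 5.2.3.2.1.

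**What happens to a failure.** SAP 5.2.3.2 substitutes the baseline value from the point of failure onward, then adds: "However, treatment failure rules for the HSSD pain related endpoints will be handle differently and are specified in Section 5.2.3.2.1".

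**The HSSD pain section.** SAP 5.2.3.2.1 has two sentences. One makes HS analgesic use within 1 day of a visit a failure, at that visit, for 24-hour and current pain. The other reads: "Treatment failure rules will not be applied throughout the study for analyses of the HSSD 7 days recall pain component".

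**The estimand.** SAP 5.2.4.1 says of continuous endpoints: "No improvement (zero change) will be assigned after a subject meets one or more treatment failure criteria". It closes with: "The composite strategy will be used for analyzing all efficacy endpoints". Protocol 9.4.1 is to the same effect: "The baseline values will be assigned regardless of the observed data for continuous endpoints". Neither names an HSSD exception.

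**Where the item is used.** SAP 5.5.7.2 compares each 7-day symptom score with placebo at Week 16. It also says: "The change from baseline in HSSD total symptom score at Week 16 will be compared". SAP 5.2.2.5.1 gives the total as "derived by averaging the 5 individual scale scores that utilize the past 7-day recall period"; worst pain over 7 days is one of the five.

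**The concern.** Not penalising analgesic use on a 7-day recall item is sensible, since a 1-day window does not fit it. But the waiver is written for treatment-failure rules in general. A participant who starts a biologic or a systemic corticosteroid for HS, or who stops study drug for lack of efficacy, keeps the observed 7-day pain score. The same participant's tenderness, itch, heat and odor scores go back to baseline. Two consequences follow.

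- The Week 16 comparison of 7-day pain answers a different question from the other four symptoms and from the stated estimand. Relief from prohibited therapy counts for the randomised arm, guselkumab or placebo.
- The HSSD total has no defined value for a failure. The comparison of participants with at least a half-SD fall in the total (SAP 5.5.7.2) inherits the gap.

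**Working it through.** The plan gives no figure to reproduce here. The check is a reading of the text followed by an illustration on stated assumptions.

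**Step 1: follow the rules for one participant who starts prohibited HS therapy before Week 16.**

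| Score | Governing text | Value after failure |
|---|---|---|
| 7-day tenderness, itch, heat, odor | SAP 5.2.3.2 | Baseline |
| 7-day pain | SAP 5.2.3.2 carve-out, then 5.2.3.2.1 | As observed |
| 7-day pain | SAP 5.2.4.1; Protocol 9.4.1 | Baseline (zero change) |
| HSSD total | No text states item level or whole score | Undetermined |

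The second and third rows cannot both be followed.

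**Step 2: can such scores reach the analysis?** The Schedule of Activities collects the HSSD at Weeks 0, 2, 4, 8, 12 and 16. Protocol 7.1 continues evaluations for about 12 weeks after the last dose. A last dose at Week 4 or later therefore allows a Week 16 score (4 + 12 = 16). A single dose at Week 0 takes follow-up only to about Week 12, but the repeated-measures model uses all visits through Week 16.

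**Step 3: one participant (assumed values).** All five 7-day items are 6 at baseline and 2 after prohibited therapy.

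- 7-day pain change: 2 − 6 = −4 under the waiver; 0 under the composite rule.
- Total, failure applied to the whole score: 0.
- Total, item by item with pain exempt: (2 + 4 × 6)/5 − 6 = 5.2 − 6 = −0.8.
- Total, no failure rule: −4.

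**Step 4: between-group shift.** The documents give neither failure rates nor the size of relief. Assume failure by Week 16 in 10–20% on placebo and 5–10% on guselkumab, and a fall of 2–4 points on the 0–10 scale in every failure. As a simple-means approximation:

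shift toward the null = (placebo failure rate − guselkumab failure rate) × fall

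- Smallest: (0.10 − 0.10) × 2 = 0.
- Middle: (0.15 − 0.05) × 3 = 0.30.
- Largest: (0.20 − 0.05) × 4 = 0.60.

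Pain has weight 1/5 in the total, so item-by-item application gives 0, 0.06 and 0.12.

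**Step 5: direction.** With 60 per arm, take 15% failure on placebo (9 participants), 5% on guselkumab (3) and a 4-point fall. The waiver improves mean 7-day pain by 0.15 × 4 = 0.60 on placebo and 0.05 × 4 = 0.20 on guselkumab, a net 0.40 against guselkumab. Swapping the rates gives 0.40 in its favour. Equal rates and equal relief give 0.

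**The case against.** **The sentence may concern analgesics only.** It directly follows the analgesic rule, the only rule that section sets out. That may well be the intent. But the wording is not limited to that rule, and 5.2.3.2 has already removed HSSD pain endpoints from the general rule. If the narrow meaning was intended, the sentence should say so.

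**A specific rule can qualify a general one.** The Protocol leaves details to the SAP, and using observed values is a legitimate treatment-policy choice. SAP 5.5.2.2, 5.5.4 and 5.5.8 also set failure rules aside, so the claim to cover all endpoints is not literal elsewhere. This softens the conflict with the Protocol. However, those analyses are presented as additional, sensitivity or exploratory. For 7-day pain the waived version is the only Week 16 placebo comparison planned, and no separate estimand is declared.

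**The illustration assumes that every failure improves.** This objection stands. Participants who stop for lack of efficacy or worsening HS may have unchanged or worse pain, and for those who are worse a reset to baseline is the kinder value. Some failures will also have no Week 16 score.

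**Stronger readings that the documents do not support.**

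- A reader might infer that the total score is exempted too. SAP 5.2.3.2.1 names only the pain component; the total is affected through the unstated level of application.
- A reader might infer a bias in favour of guselkumab. Relief in a placebo participant is credited to placebo, and under the rates assumed here the shift is zero or against guselkumab.
- A reader might extend the waiver to the 24-hour pain endpoint. The quoted sentence does not touch it. Whether the general criteria still apply there after the carve-out is a separate question.

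**Conclusion.** The text is wrong as written: SAP 5.2.3.2.1, read with 5.2.3.2, cannot be reconciled with SAP 5.2.4.1 or Protocol 9.4.1 for 7-day recall pain. The mixed total score is conditional on item-by-item application, which the SAP neither states nor excludes.

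Under the assumed rates and relief, the 7-day pain difference moves by 0 to 0.6 points toward the null, and the total by 0 to 0.12. The shift is smaller where failures do not improve, and it reverses if failure is commoner on guselkumab.

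The consequence is limited. The 7-day items and the total are other secondary endpoints with nominal p-values, outside the eight-hypothesis testing scheme. The primary endpoint is unaffected. The point merits correction because a listed secondary endpoint departs from the plan's own estimand and the remedy is cheap.

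**What to change.** Replace the sentence in SAP 5.2.3.2.1 with text such as:

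*The analgesic treatment failure rule will not be applied to the HSSD 7-day recall pain item. All other treatment failure rules (stopping study intervention for lack of efficacy or for an AE of worsening HS, and starting prohibited medication or therapy other than analgesics) apply to this item and to the HSSD total symptom score as a whole.*

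The words 'other than analgesics' are needed: SAP 5.2.3.1 lists HS analgesics among the prohibited therapies, so an unqualified reference would bring the analgesic rule back.

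Keep the observed-data analysis of 7-day pain as a sensitivity analysis. If the sponsor does want observed values as the main analysis, SAP 5.2.4.1 should declare a separate estimand for this item, and the level at which failure applies to the total must still be stated.

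The cost is a short SAP edit and minor programming, with no new data. It should be made before the Week 16 database lock, after which selected sponsor personnel are unblinded.

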5.2.3.3. Missing Data Imputation

For the following binary and continuous composite endpoints, participants with missing data on component(s) but not all components, a last observation carried forward (LOCF) imputation will be performed for the missing component(s) and response status or change from baseline will then be determined.

- HiSCR (abscess, inflammatory nodule, and draining fistula counts)
- Endpoints related to total AN count (abscess and inflammatory nodule counts)
- Endpoints related to total inflammatory and non-inflammatory nodule counts
- HSSD total symptom score (pain, tenderness, hot skin feeling, odor, and itchiness)

After the treatment failure rules are applied, the remaining missing data will be handled as follows for all of the efficacy analyses including the analyses at key visit Week 16 and over time *unless otherwise specified*.

5.2.3.3.1. Missing Data Binary Endpoints

For binary efficacy endpoints, participants with missing response status will be considered non-responders for all of the efficacy analyses at key visit of Week 16 and over time summaries.

5.2.3.3.2. Missing Data Remain as Missing for Continuous Endpoints

For continuous endpoints for which longitudinal data were collected prior to the analysis visits, efficacy analyses or over time summaries are performed using a Mixed-Effect Model Repeated Measures (MMRM) model and all available data from the 3 treatment groups through Week 16 or from Week 16 through Week 48 will be included. Missing data will not be imputed after treatment failure rules are applied. Under the assumption of MAR, the missing data will be accounted for through correlation of repeated measures in the model.

For the MMRM model, an unstructured covariance matrix for repeated measure within a subject will be used. In case that convergence cannot be achieved, first order Autoregressive Moving Average will be used.

In addition, for the continuous endpoints with no post baseline data scheduled to be collected prior to the analysis visit (eg, change from baseline in DLQI at Week 16), under the assumption of missing at random (MAR), multivariate response modeling approach will be performed with SAS Proc Mixed. With this approach, baseline and post-baseline AN count data that potentially can be predictive of missingness will be included in the model and marginal means of change from baseline will be compared between the treatment groups.

In addition, no imputation will be done with missing data for efficacy analyses and over time summaries for other continuous endpoints.

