1.3. Schedule of Activities (SoA)

From Screening the	rough Week 48														
Period			Plac	ebo-Con	trolled P	eriod		Bli	nded Act	ive Treat	ment Per	riod		Safety Fo	ollow-up
Week	Screening ^a	0	2	4	8	12	16	20	24	28	32	36	40	44	48 or Early Termination Visit ^b
Study Procedures ^c				•	•			•	•		•	•		•	
Screening/Adminis	trative														
Informed consent	X														
Medical history and demographics	X														
Inclusion/ exclusion criteria	X	X													
Nicotine Use		X					X						X		
Alcohol Use		X					X						X		
Study Intervention	Administration	n													
Randomization		X					X ^d								
Study intervention IV administration ^e		X		X	X										
Study intervention SC administration ^e		X		X	X	X	X	X	X	X	X	X			
Safety Assessments															
Physical examination (including skin)	X														X
Vital signs	X	X	X	X	X	X	X	X	X	X	X	X	X	X	X
Waist Circumference		X													X
Tuberculosis evaluation	X	XX									X				
Columbia-Suicide Severity Rating Scale (C-SSRS) ^f	X	X	X	X	X	X	X	X	X	X	X	X	X	X	X
Chest radiograph	X														
12-lead ECG	X														

Period			Plac	ebo-Con	trolled Po	eriod		Bli	nded Act	ive Treat	ment Per	riod		Safety Fo	ollow-up
Week	Screening ^a	0	2	4	8	12	16	20	24	28	32	36	40	44	48 or Early Termination Visit ^b
Study Procedures ^c			I	l				I.		1					J
Urine pregnancy test ^g	X	X		X	X	X	X	X	X	X	X	X			X
Height		X													
Weight		X					X								X
Concomitant therapy		X													X
Adverse events		X													X
Efficacy Assessmen	its														
Hurley stage	X	X					X						X		
Lesion Counts	X	X	X	X	X	X	X	X	X	X	X	X	X	X	X
HS-IGA	X	X	X	X	X	X	X	X	X	X	X	X	X	X	X
DLQI ^f		X					X						X		
HADS ^f		X					X						X		
Hidradenitis Suppurativa Symptom Diary (HSSD) ^f		X	X	X	X	X	X						X		
Patient global impression of change (PGIC) of HS severity ^f			X	X			X						X		
Photographs of skin lesions ^h		X					X						X		
Clinical Laborator	y Assessment		•												
QuantiFERON®- TB test ⁱ	X														
Hepatitis B and C serology	X														
HIV antibody test	X														
Hematology	X	X					X						X		X

From Screening through Week 48															
Period		Placebo-Controlled Period					Blinded Active Treatment Period					Safety Follow-up			
Week	Screening ^a	0	2	4	8	12	16	20	24	28	32	36	40	44	48 or Early Termination Visit ^b
Study Procedures ^c															
Chemistry	X	X					X						X		X
Lipid panel ^j		X													
High sensitivity C- reactive protein (hs-CRP)		X		X			X						X		

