8.1.2. Lesion Counts

Lesion counts are defined as the counting of abscesses, inflammatory nodules, non-inflammatory nodules, draining fistulas, and non-draining fistulas. Lesions will be counted during each visit.

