5.4.2. Analysis Methods

5.4.2.1. The Change from Baseline in Total AN Count at Week 16

For the change from baseline in AN count at Week 16, treatment comparisons will be performed using a Mixed-Effect Model Repeated Measures (MMRM) Model. The MMRM model will include baseline weight (≤ 95 kg, >95 kg), baseline Hurley stage status baseline values, visit, treatment group by visit interaction, and baseline value by visit interaction as explanatory factors.

The model will be performed based on all available data from the 3 treatment groups through Week 16. The treatment difference between a guselkumab group and the placebo group will be estimated by the difference in the least squares means (LSmeans). The 95% CIs for the differences in LSmeans and p-values will be calculated.

5.4.2.2. The Change from Baseline in DLQI at Week 16

The change from baseline in DLQI at Week 16 will be analyzed based on a mixed model (Section 5.2.3.3.2). under the assumption of missing at random (MAR). Marginal mean model will account for treatment group, baseline weight (≤ 95 kg, >95 kg), baseline Hurley stage status, baseline DLQI score, and AN count at each visit up to Week 16 through correlations among these variables. Marginal means will be compared between each of the guselkumab groups and placebo.

In addition, treatment differences and their associated 95% confidence intervals will be presented.

5.4.2.3. The Change from Baseline in HS-related Skin Pain in the Past 24 Hours Based on HSSD at Week 16.

The change from baseline in HS-related skin pain in the past 24 hours based on HSSD at Week 16 will be analyzed based on the analysis approach as specified in Section 5.4.2.1.

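### If the unstructured MMRM does not converge, the SAP's only fallback assumes one common variance at all visits, so the Week 16 standard errors for AN count and 24-hour pain may be too small or too large

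*SAP*

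**What the plan says.** SAP 5.2.3.3.2 states that for the MMRM "an unstructured covariance matrix for repeated measure within a subject will be used". If that fit fails, "In case that convergence cannot be achieved, first order Autoregressive Moving Average will be used". The section imputes nothing after the treatment failure rules and relies on the covariance model under MAR: "the missing data will be accounted for through correlation of repeated measures in the model".

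SAP 5.4.2.1 applies this model to change in AN count at Week 16: "The model will be performed based on all available data from the 3 treatment groups through Week 16". SAP 5.4.2.3 sends the 24-hour pain endpoint to the same model: it "will be analyzed based on the analysis approach as specified in Section 5.4.2.1". In the Schedule of Activities (Protocol 1.3), lesion counts and the HSSD both fall at Weeks 0, 2, 4, 8, 12 and 16.

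Neither document names a heterogeneous-variance structure, an ordered list of structures or a robust standard error. The protocol names no covariance structure at all.

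**The concern.** ARMA(1,1) has three parameters: one variance, one autoregressive and one moving-average. It cannot let Week 16 have a different residual variance from Week 2. Only the Week 16 contrast is tested, yet its model-based standard error would come from a variance pooled over five visits. A larger sample does not remove that error.

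The plan's own rules make equal variances doubtful, although this is inference and not a documented fact. SAP 5.2.3.2 holds treatment failures at zero change from the failure onward while other participants continue to change. For pain, SAP 5.2.3.2.1 applies a failure rule visit by visit, according to recent analgesic use.

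Two of the three major secondary endpoints use this model. With two doses, that is four of the six major secondary comparisons, each tested at two-sided 0.05 in the SAP 5.2.1.1 sequence. Too small a standard error could pass a gate falsely; too large a one could close it.

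**Working it through.** **The plan's own figure.** The documents give no SD, standard error or power for AN count or pain. The only stated design figures are the HiSCR powers in Table 1. For row 5 (25% vs 55%, 60 per arm, pooled null variance, no continuity correction):

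- Null SE = sqrt(2 × 0.40 × 0.60 / 60) = 0.0894.
- Alternative SE = sqrt((0.25 × 0.75 + 0.55 × 0.45) / 60) = 0.0851.
- Power = Phi((0.30 − 1.96 × 0.0894) / 0.0851) = Phi(1.46) = 92.9%, against 93% stated.

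The six rows reproduce as 84.1, 94.1, 98.4, 81.6, 92.9 and 98.0, against 85, 94, 98, 82, 93 and 98. This confirms the sample size inputs but says nothing about the MMRM.

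**Inputs from the documents.** Post-baseline visits at Weeks 2, 4, 8, 12 and 16, so gaps of 2, 4, 4 and 4 weeks (baseline is a covariate, not a repeated outcome); 60 per arm, three arms; two-sided 0.05. Unstructured parameters: 5 × 6 / 2 = 15.

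**Inputs assumed.** Visit SDs, correlations and dropout.

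**Step 1: hand approximation, near-complete data.** SE ratio = sqrt(mean of the five visit variances) / Week 16 SD. Type I error = 2 × (1 − Phi(1.96 × ratio)).

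| Assumed SDs, Weeks 2/4/8/12/16 | Ratio | Type I error |
|---|---|---|
| 6/6.5/7/7.5/8 | sqrt(49.5)/8 = 0.879 | 8.5% |
| 4/5/6/7/8 | sqrt(38)/8 = 0.771 | 13.1% |
| 8/7.5/7/6.5/6 | sqrt(49.5)/6 = 1.173 | 2.2% |

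**Step 2: best-fitting ARMA(1,1).** The structure was fitted to assumed true covariances whose correlations decline with time, with 0%, 10% and 20% monotone dropout and Week 16 SD set to 1. With complete data the actual SE is sqrt(2/60) = 0.183.

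| SD profile | Model SE / actual SE | Type I error |
|---|---|---|
| Equal | 0.999 to 1.001 | 5.0% |
| Rising 0.8 to 1 | 0.89 to 0.90 | 7.6% to 8.0% |
| Rising 0.6 to 1 | 0.80 to 0.82 | 10.9% to 11.8% |
| Falling 1.25 to 1 | 1.13 to 1.14 | 2.6% to 2.7% |
| Falling 1.5 to 1 | 1.25 to 1.27 | 1.3% to 1.4% |

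The equal-SD row isolates spacing. Indexing correlation by visit number instead of by week moves the Week 16 SE by about 0.1%, even with 20% dropout. Essentially all the error comes from the common variance.

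**Step 3: REML simulation.** 300 trials per profile, 3 × 60, 10% dropout, no true effect.

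| SD profile | Mean model SE | Empirical SE | Rejection |
|---|---|---|---|
| Equal | 0.186 | 0.187 | 6.7% |
| Rising 0.6 to 1 | 0.151 | 0.183 | 9.3% |
| Falling 1.5 to 1 | 0.236 | 0.192 | 1.7% |

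The Monte Carlo error of a 5% rate in 300 runs is sqrt(0.05 × 0.95 / 300) = 1.3 points, so 6.7% is compatible with 5%. The SE columns are the more precise comparison.

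**Step 4: a heterogeneous alternative.** Index-based heterogeneous AR(1), with five variances and one correlation, gives ratios of 1.005 to 1.022 and type I error of 4.5% to 4.9% in all five profiles at 0% to 20% dropout (one correlation pattern).

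**The case against.** The strongest reply is that the fallback will probably never be used for these tests. Fifteen parameters on about 180 participants is an easy fit. In a trial run with assumed inputs (3 × 60, SDs rising 4 to 8, 8% treatment failures set to zero change, 3% intermittent missingness, 10% to 30% dropout), the unstructured REML fit converged in 75 of 75 data sets. That was not the SAS procedure, but it supports expecting convergence. This stands: the percentages above apply only if the fit fails, and they are not the trial's overall error rate.

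The SAP also fixes its fallback in advance, so analyst discretion is not the problem. The consequence is limited too. The CMH test on HiSCR alone decides whether the study is positive, DLQI has a separate multivariate model, and SAP 5.2.1 accepts an overall type I error of up to 0.1 in this proof-of-concept study. All of that stands, and it limits the weight of the point. It does not remove it, because a fallback should keep the test valid in the event for which it is written.

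A reader might infer two stronger claims. One is that the AN count and pain p-values would definitely miss 0.05 under the fallback. The documents give no visit SDs, so neither the existence, the direction nor the size of the error can be established. The other is that uneven visit spacing is a cause in its own right. Only one of the four gaps differs, and its effect is about 0.1%.

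**Conclusion.** The point holds as a conditional weakness of low weight. If the unstructured model fails and residual SDs differ by visit, the Week 16 SE for AN count and 24-hour pain is biased. It is too small if SDs rise (type I error about 8% to 13%) and too large if they fall (about 1% to 3%). These figures rest on assumed SD profiles, correlations and dropout. With equal SDs there is no error, and if the unstructured model converges, as expected, the question does not arise.

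The same fallback sentence covers the Week 16 to 48 lesion-count models in SAP 5.5.2.2. These have nine visits, hence 9 × 10 / 2 = 45 unstructured parameters, with placebo split into two groups of about 30. Non-convergence is more plausible there, but those models feed only descriptive confidence intervals.

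**What to change.** In SAP 5.2.3.3.2, replace the ARMA(1,1) fallback with a structure that has visit-specific variances: for example heterogeneous Toeplitz (5 + 4 = 9 parameters for five visits), then heterogeneous AR(1) (6 parameters) if that also fails. Settle this before the Week 16 lock and unblinding, so that the choice cannot depend on results.

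A sandwich standard error is an optional alternative safeguard. It targets the actual SE under a wrong covariance, but it does not repair the MAR estimate's own dependence on the covariance model. A long list of structures plus a compulsory sandwich SE would be more than the problem needs.

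The cost is one SAP sentence and a few more covariance parameters than ARMA(1,1)'s three. Nothing changes if the unstructured model converges.
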